### 1.2.1 Clinical Studies

A first-in-human, randomized, double-blind, placebo-controlled study (Protocol AT-02A-001) was conducted in 65 healthy adults to investigate the safety, tolerability, and PK of AT-752. Single doses up to 1500 mg and multiple doses (1000 mg QD x 7 days; 750 mg BID x 4.5 days; 750 mg BID x 4.3 days) were evaluated. Based on the human PK results obtained from this study, an AT-752 dose of 750 mg TID (starting dose for the current study) is anticipated to demonstrate antiviral activity in dengue patients. In healthy subjects, this regimen rapidly achieved plasma concentrations of AT-273, considered plasma surrogate for the intracellular active triphosphate metabolite AT-9010, in excess of 200 ng/mL (in vitro EC90 of AT-281 against DENV-2 is 0.64 μM or approximately 200 ng/mL equivalent of AT-273) and maintained through concentrations consistently above this threshold throughout the treatment duration ([Figure 1-2](#)).

**Figure 1-1 Mean (+SD) Plasma Concentration-Time Profile of AT-273, Surrogate of the Intracellular Active Triphosphate Metabolite AT-9010, Following Oral Administration of 750 Mg TID of AT-752 Under Fasted Conditions in Healthy Participants (AT-02A-001 Cohort 3b; N=6)**

Furthermore, a high-fat/high-calorie meal did not impact the total exposure of AT-281 while slightly increasing plasma exposure of AT-273. Therefore, AT-752 can be dosed without or with a meal. Also, plasma exposure of AT-273 was similar between a separately enrolled ethnic cohort of healthy participants with southeast Asian origins and the general population (Cohort 3a), whereas plasma exposure of AT-281, AT-551, and AT-229 was numerically higher by 20-30%, which is within the expected variability for the drug. Dose adjustment is not expected for this ethnic group.

AT-752 was well tolerated after either single or multiple doses in healthy subjects. Other than a single subject who withdrew consent, all other subjects completed the study. There were no SAEs reported. Most AEs were Grade 1 (mild) in intensity and no AEs of  $\geq$  Grade 3 severity were reported. The most common AEs across both parts of the study were headache, nausea, and vomiting. GI-related events (e.g., nausea, vomiting, abdominal pain, diarrhea, and constipation) were observed more commonly with AT-752 as compared to placebo. Vomiting appeared to increase with increasing AT-752 dose level ( $\geq$ 750 mg), although cases were mild/moderate in intensity and were self-limiting or managed with ondansetron. Most changes in laboratory parameters were mild (Grade 1) with no apparent relationship between

the incidence of any laboratory toxicity and AT-752 dose level. Clinically significant changes were not reported for ECG parameters.

Additional details on this study can be found in the investigator's brochure v 2.0 ([Atea Pharmaceuticals](#)).

### **1.3 RATIONALE FOR STUDY**

Dengue is caused by 4 distinct types of RNA viruses (DENV-1, DENV-2, DENV-3, and DENV-4) belonging to the flavivirus genus. Although a vaccine is available, its efficacy is variable between the different serotypes and it is only indicated for individuals with a history of previous DENV infection. There are no effective therapeutics for dengue, and treatment options are limited to supportive care such as fluid replacement and clinical monitoring. A safe and effective antiviral therapy that targets all DENV serotypes is greatly needed to reduce the global burden of this disease and meet this unmet medical need.

Atea Pharmaceuticals is developing a novel purine nucleotide prodrug, AT-752, which is designed to treat patients that have been infected with the DENV. Supported by tolerability/safety and PK in healthy subjects (see [Section 1.2.1](#)), the next logical development step for a dengue treatment is to evaluate safety, antiviral activity and PK/PD relationships of differing doses of AT-752 in DENV-infected patients. This study will evaluate the safety, PK, and PD of AT-752 in adult patients with confirmed DENV infection and further support dose selection for subsequent, later phase trials.

### **1.4 RATIONALE FOR DOSE SELECTION**

The dose levels selected for the study described herein are:

- Cohort 1: 750 mg AT-752/placebo 3 times a day (TID) for 5 days
- Cohort 2: up to 1000 mg AT-752/placebo twice a day (BID) or TID for 5 days
- Cohort 3: up to 1500 mg AT-752/placebo BID for 5 days

Based on the PK results of the AT-02A-001 study (see [Section 1.2.1](#)), the AT-752 starting dose of 750 mg TID (2250 mg total daily dose) is anticipated to demonstrate antiviral activity in dengue patients. This dose rapidly achieved and maintained plasma AT-273 troughs above the target 200 ng/mL (in vitro EC90 of AT-281 against DENV-2 is 0.64 µM or approximately

200 ng/mL equivalent of AT-273). Starting from the second dose, 75% of individual AT-273 troughs were above this threshold.

CCI [REDACTED]

CCI [REDACTED]

CCI [REDACTED]

A large, stylized watermark consisting of the letters 'C', 'C', and 'I' in a bright red color, set against a solid black rectangular background. The letters are thick and have a slightly irregular, hand-drawn appearance.

## **2. STUDY OBJECTIVES**

The primary objective of this study is:

- To investigate the antiviral activity of AT-752 versus placebo in terms of reduction of DENV RNA from baseline in adult subjects with confirmed DENV infection

The secondary objectives of this study include PK and safety objectives as outlined below.

The PK objective of this study is:

- To evaluate the PK of AT-752 (AT-281) and metabolites in adult subjects with confirmed DENV infection.

The safety objective of this study is:

- To evaluate safety of AT-752 versus placebo in adult subjects with confirmed DENV infection

The exploratory objectives of this study include PD objectives as outlined below:

[figure not shown]
- To describe the effect of AT-752 on viremia (viral titre), DENV nonstructural protein 1 (NS1) levels, fever, and biomarkers (see list in [Section 8.3.4](#)) compared to placebo in adult subjects with confirmed DENV infection

### 3. STUDY DESIGN

This study evaluates the safety, PK, and PD of AT-752 will enroll approximately 60 subjects that meet the inclusion/exclusion criteria. Following screening and informed consent, eligible subjects will be randomized to receive either AT-752 or matching placebo orally TID for 5 days in Cohort 1 of the study. Subsequent cohorts will receive AT-752/placebo either BID or TID, as described in [Figure 3-1](#). Randomization will be stratified by geographic region. Standard-of-care treatment, including acetaminophen, will be permitted during the study.

A schematic of the study design is provided in [Figure 3-1](#).

**Figure 3-1 AT-02A-002 Study design**

At screening, information including demographics, medical history (including time since illness onset), and concomitant medications will be gathered from potential subjects. Additional assessments and collection of data will be conducted as indicated in the schedule of events (SOE; [Table 3-1](#)). Any clinical care necessary throughout the study, such as supportive care, will be at the discretion of the investigator and institutional guidelines. After subjects are confirmed eligible at screening, randomization and the initial dosing should

occur within 24 hours, and if possible, the initial dose should be given on the same day as screening.

Upon randomization, subjects will receive their first dose of study drug. Subjects in Cohort 1 will receive doses that are separated by approximately 8 hours ( $\pm 2$  hours; morning, mid-day, and evening). [Subjects receiving BID dosing will receive doses that are separated by 12 hours ( $\pm 2$  hours; morning and evening)]. Subjects can continue participation even if hospitalized or using mobile nursing during the study, depending on site availability and subject decision. Subjects will be discharged on Day 6 (after end of treatment) if hospitalized, and asked to return on Day 7, Day 8, and Day 14 ( $\pm 1$  day) with a final safety follow-up performed on Day 28 ( $\pm 3$  days). For clinical sites that decide to use mobile nursing, some of the subsequent visits (Days 2-5, Days 7-8, and Day 14) may be performed at investigator discretion through mobile nursing. The Day 1, Day 6, and Day 28 visits must be conducted at the clinical site. The Day 6 end of treatment visit will occur 8 to 24 hours after the last dose of study medication is administered.

Note that if the initial dose of study drug is administered on the same day as screening (at mid-day or in the evening), the last dose of study drug will be administered on Day 6. See [Section 3.1.2](#) and [Section 3.1.3](#) for detailed descriptions of TID and BID dosing, respectively.

The 3 planned sequential dosing cohorts are:

- Cohort 1: 750 mg AT-752/placebo TID for 5 days
- Cohort 2: up to 1000 mg AT-752/placebo BID or TID for 5 days
- Cohort 3: up to 1500 mg AT-752/placebo BID for 5 days

In each blinded cohort, subjects will be randomized to receive active drug or placebo in a 3:1 randomization. Each cohort will include 20 subjects (15 subjects receive AT-752 and 5 subjects receive placebo).

Specific doses for Cohort 2 and Cohort 3 will be endorsed by the SRC) after an unblinded review of the previous cohort by the SRC. Prior to the initiation of each cohort after Cohort 1, all safety and available PK data through at least 5 days in the current dose cohort will undergo an unblinded review by the SRC. Following each SRC review, the dose for the next cohort will be endorsed by the SRC and the cohort enrolled according to schedule outlined in the SOE ([Table 3-1](#)).

### 3.1 SCHEDULE OF ASSESSMENTS

**Table 3-1 Schedule of Events**

Assessment	Screening	Treatment Period			Follow-up				
		Day 1	Days 2-4	Day 5	Day 6	Day 7	Day 8	Day 14±1	Day 28 ±3/ EOS (Early Termination)
Visit Type	Site	Site	Site or Mobile	Site or Mobile	Site	Site or Mobile	Site or Mobile	Site or Mobile	Site
Eligibility criteria	X								
Informed consent a	X								
Demographics	X								
Medical history	X								
Concomitant medications	X	X	X	X	X	X	X	X	X
Physical examination b	X	X	X	X	X	X	X	X	X
Vital signs c	X	X	X	X	X				
12-lead ECG (triplicate-consecutive)	X				X				X
Chemistry/hematology/coagulation d	X	X	Day 2, 4		X		X	X	X
Urinalysis w/ microscopy d	X	X			X		X		
SARS-CoV-2 rapid test, RIDT e	X				X				
Pregnancy testing f	X								
NS1 rapid test g	X								
Pharmacokinetic assessments h		X	Day 2 and Day 3 or 4						
DENV serotype testing i	X								
Viral load j	X	X	X	X	X	X	X	X	X (Day 28 only)
NS1 antigen test	X	X	X	X	X	X	X	X	X (Day 28 only)

Plasma Biomarker	X	X	Day 2, 4		X		X	X	X (Day 28 only)
Adverse events k	X	X	X	X	X	X	X	X	X
Randomization	Prior to dosing								
Study drug administration		X	X	X					
Accountability of returned drug, and review of patient diary					X				X (Early Termination only)

Abbreviations: DENV = dengue virus; ECG = electrocardiogram; ELISA = enzyme-linked immunosorbent assay; NS1 = nonstructural protein 1; RIDT = rapid influenza diagnostic test

- a. Informed consent will be performed before any study procedures are conducted. Results from standard of care evaluations that are available prior to informed consent are accepted if performed within 24 hours of screening
- b. A full physical examination, including height and weight, will be performed at screening and Day 28, except height will not be collected at Day 28. Symptom-directed physical examinations will be performed at the remaining visits.
- c. On Day 1, vital signs should be collected pre-administration of study drug. Vital sign measurements should be performed before any scheduled blood collections. On subsequent days (Days 2-6), vital signs can be collected at any time.  
In addition, temperature readings will be performed at least 4 times daily, in the morning, mid-day, late afternoon, and evening (approximately every 4 hours while the subject is awake) through the end of treatment. Temperature will be measured orally and will be recorded in a patient diary (and given to the site coordinator for entry in the eCRF).
- d. Hematology/ chemistry/ coagulation to include complete blood count (CBC) including white blood cell (WBC) count with differential count, red blood cell (RBC) count, platelet count, hemoglobin, hematocrit, and RBC indices; aspartate transaminase (AST), alanine aminotransferase (ALT), total and direct bilirubin, alkaline phosphatase, blood urea nitrogen (BUN), creatinine, serum creatine kinase, lipase, bicarbonate or total carbon dioxide, sodium, potassium, chloride, glucose, total protein, albumin, phosphate, calcium, and amylase; international normalized ratio (INR), prothrombin time, and partial thromboplastin time. Urinalysis will be performed with microscopy at indicated visits but treatment with study drug may begin before the screening results have been obtained unless medically required to establish eligibility (at investigator's discretion). Additional urinalysis may be performed as clinically indicated.  
One-time retests of individual screening laboratory parameters or assessments may be permitted in certain scenarios. Such scenarios may include lab processing error, results inconsistent with subject's historical values/medical history, or other extenuating circumstances such as a recent or intercurrent illness potentially affecting screening laboratory results. Standard of care laboratory results prior to informed consent are accepted if performed within 24 hours of screening.
- e. SARS-CoV-2 rapid test performed at screening and Day 6. RIDT performed only at screening.
- f. A dipstick pregnancy test is required at screening. Additional pregnancy tests may be performed locally as clinically indicated.
- g. Rapid point of care (POC) test for DENV NS1 antigen. See [Section 3.1.4](#) for details about assay timing.
- h. Pharmacokinetic (PK) plasma samples will be collected on Day 1 at time 0 (pre-dose; before the first dose on Day 1) and 24 hours after Dose 1. For TID dosing, samples will be obtained before Dose 7 and 0.5, 1, 2, 4, and 6 hours after Dose 7. This serial PK sampling for TID dosing may be done for Dose 7, 8, or 9, based on site/patient convenience. For BID dosing, samples will be obtained before Dose 5 and 0.5, 1, 2, 4, 6, and 8 hours after Dose 5. This serial PK sampling for BID dosing may be done for Dose 5, 6, or 7, based on site/patient convenience. For blood samples, a ± 10-minute window for time points ≤4 hours; ± 15 minute for time points between 4 and 24 hours. PK samples will also be obtained at any early study discontinuation visits. The timing of these PK samples relative to the last 2 (most recent) doses will be recorded. See [Section 3.1.4](#).
- i. Subjects can begin treatment with study drug before the DENV-serotype results are obtained.

- 
- j. Measurement of plasma viremia by viral titre and using a serotype-specific, real-time reverse transcription polymerase chain reaction (RT-PCR) assay. Subjects can begin treatment before the viral load results are obtained. See [Section 3.1.4](#) for details about the timing of this assay.
- k. Adverse events are collected beginning at screening. Treatment-emergent adverse events and serious adverse events will be assessed from the time of study drug dosing until end of study and should be followed until they are resolved, stable, or judged by the investigator to be not clinically significant.
- l. After subjects are confirmed eligible at screening, randomization and the initial dosing should occur within 24 hours, the initial dose should be given on the same day as screening, if possible. TID dosing at screening/Day 1 can begin in the morning, at mid-day, or in the evening (see [Section 3.1.2](#). BID dosing on Screening/Day 1 can begin in the morning or the evening (See [Section 3.1.3](#)).  
Note that if the initial dose of study drug is administered on the same day as screening (at mid-day or in the evening), the last dose(s) of study drug will be administered on Day 6.
- 

### 3.1.1 Screening/Day 1

After eligibility is determined at screening, the initial dose of study drug can be administered after randomization and within 24 hours of screening. This can occur before obtaining the results of the DENV serotype testing and viral load assessments. If possible, administer the initial dose of study drug on the same day as screening.

Evaluations that must be completed before administering the initial dose include:

- Determining eligibility criteria
- Obtaining informed consent
- Recording demographics, medical history, and concomitant medications
- Complete physical examination. If the initial dose of study drug is administered on the same day as screening, the results of the complete physical examination at screening will be substituted for symptom-directed physical examination on Day 1
- Vital signs. On Day 1, vital sign measurements should be performed before any scheduled blood collections and prior to administration of study drug. If the initial dose of study drug is administered on the same day as screening, the results of the vital signs obtained at screening will be used for the Day 1 vital sign results. Note that oral temperature is also to be collected during the dosing period at least 4 times a day (morning, mid-day, late afternoon, evening; approximately every 4 hours while subjects are awake)
- Triplicate consecutive 12-lead ECG.

- Chemistry, hematology, coagulation, and urinalysis (with microscopy). At screening, samples should be collected for urinalysis (with microscopy), but subjects can begin treatment with study drug before the results are obtained unless medically required to establish eligibility (at investigator's discretion). If the initial dose of study drug is administered on the same day as screening, the screening results for these tests will be used for the Day 1 results. Results from standard-of-care evaluations that are available prior to informed consent are accepted if performed within 24 hours of screening
- SARS-CoV-2 rapid test, rapid influenza diagnostic test, and urine pregnancy testing
- DENV serotype testing. Subjects can begin treatment with study drug before the DENV-serotype results are obtained, but the samples should be obtained before dosing
- Viral load. Measurement of plasma viremia by viral titre and using a serotype-specific, real-time RT-PCR assay. Subjects can begin treatment with study drug before the DENV-serotype results are obtained, but the sample should be obtained prior to dosing. If the initial dose of study drug is administered on the same day as screening, the screening results for viral load will be used for the Day 1 values
- NS1 antigen detection test. If the initial dose of study drug is administered on the same day as screening, the screening results for NS1 antigen will be used for the Day 1 values
- Adverse events. AEs will be collected from screening to end of study (EOS)
- Randomization. Randomization will be stratified by geographic region

### **3.1.2 Timing of TID Dosing**

If possible, the first dose of study medication should be administered on the same day as screening.

The first dose of study medication (on Day 1) must be taken under observation at the study site. All other doses will be administered at the study site for subjects who are confined to the site during the study, or will be self-administered outside the study site (e.g., at home) for subjects at sites that choose to use mobile nursing (except the doses administered prior to PK evaluation [Dose 7, 8, or 9; see [Section 3.1.4](#)], which must be taken under observation at

the study site, or under observation by mobile nursing staff as applicable). The timing of the doses will be recorded in a patient diary.

The first dose of study medication should be administered between 6 AM and 4 PM, inclusive or between 8 PM and 10 PM, inclusive. Dosing after 4 PM but before 8 PM would make scheduling for the second dose difficult, considering the later hours.

The second dose of study medication must be taken after at least 6 hours and no later than 10 hours after the first dose, allowing the participant to select a convenient 8-hour ( $\pm 2$  hours) dosing schedule thereafter to complete a total of 15 doses.

For example, if a patient intends to choose a 6 AM, 2 PM, 10 PM dosing schedule:

- Then if the first dose is administered between 6 AM and 8 AM on Day 1, the second dose should be administered at 2 PM on Day 1 and the third dose at 10 PM on Day 1, and the subject can then proceed with the 6 AM, 2 PM, and 10 PM dosing schedule on Day 2 and thereafter.
- Or if the first dose is administered between 8 AM and 10 AM on Day 1, the second dose should be administered at 4 PM on Day 1 and the third dose at 10 PM on Day 1, and the subject can then proceed with the 6 AM, 2 PM, and 10 PM dosing schedule on Day 2 and thereafter.
- Or if the first dose is administered between 10 AM and noon on Day 1, then the second dose should be administered at 8 PM on Day 1, and the subject can then proceed with the 6 AM, 2 PM, and 10 PM dosing schedule on Day 2 and thereafter.
- Or if the first dose is administered between noon and 4 PM on Day 1, the second dose should be administered at 10 PM on Day 1, and the subject can then proceed with the 6 AM, 2 PM, and 10 PM dosing schedule on Day 2 and thereafter.
- Or if the first dose is administered between 8 PM and 10 PM on Day 1, the subject can then proceed with the 6 AM, 2 PM, and 10 PM dosing schedule on Day 2 and thereafter.

Doses of AT-752 and matching placebo should be separated by 8 hours ( $\pm 2$  hours). After Day 1, if a dose is delayed, it should be taken as soon as possible, but must be taken at least 6 hours before the next scheduled dose. Otherwise, the dose must be skipped, and the next dose

taken as scheduled. Dosing will be stopped at the end of the 15-dose treatment period. At the end of the treatment period, the tablets from any missed doses should be returned to the site.

Treatment adherence will be assessed by a study medication log (patient diary), which will be completed by the clinic staff for in clinic doses and by the participant for out of clinic doses.

### **3.1.3 Timing of BID Dosing**

If possible, the first dose of study medication should be administered on the same day as screening.

The first dose of study medication (on Day 1) must be taken under observation at the study site. The doses for PK evaluation (for Dose 5, 6, or 7; see Section 3.1.4) must also be taken under observation at the study site, or under observation by mobile nursing staff as applicable.

All other doses may be administered either at the study site or will be self-administered outside the study site (e.g., at home). The timing of the doses will be recorded in a patient diary.

The second dose of study medication must be taken after at least 6 hours and no later than 12 hours after the first dose, allowing the participant to select a convenient 12-hour ( $\pm 2$  hours) dosing schedule thereafter to complete a total of 10 doses. For example,

- If the first dose of study medication is administered between 6AM and 1 PM on Day 1, the second dose should be administered between 6 PM and no later than 10PM on Day 1, and then the subject can begin their preferred 12-hour dosing schedule on Day 2 (e.g., 6 AM and 6 PM, OR 7 AM and 7 PM, OR 8 AM or 8 PM, etc.), as long as the 12 hours ( $\pm 2$  hours) timing of doses is adhered to.
- Or if the first dose of study medication is administered between 1 PM and 4 PM on Day 1, the second dose should be administered at 10 PM on Day 1, and then the subject can begin their preferred 12-hour dosing schedule on Day 2 (eg, 6 AM and 6 PM, OR 7 AM and 7 PM, OR 8 AM or 8 PM, etc), as long as the 12 hours ( $\pm 2$  hours) timing of doses is adhered to.
- Or if the first dose of study medication is administered between 6 PM and 10 PM on Day 1, the subject can then begin their preferred 12-hour dosing schedule on Day 2

(e.g., 6 AM and 6 PM, OR 7 AM and 7 PM, OR 8 AM or 8 PM, etc.), as long as the 12 hours ( $\pm 2$  hours) timing of doses is adhered to.

Doses of study drug should be separated by 12 hours ( $\pm 2$  hours). After Day 1, if a dose is delayed, it should be taken as soon as possible, but must be taken at least 6 hours before the next scheduled dose. Otherwise, the dose must be skipped, and the next dose taken as scheduled. Dosing will be stopped at the end of the 10-dose treatment period. At the end of the treatment period, the tablets from any missed doses should be returned to the site.

Treatment adherence will be assessed by a study medication log (patient diary), which will be completed by the clinic staff for in clinic doses and by the participant for out of clinic doses.

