## **5. STUDY TREATMENTS**

### **5.1 TREATMENTS ADMINISTERED**

All subjects will receive the study treatments as described in [Section 3](#). The time of the initial study drug administration will be called “0” hours. The study drug will be administered with approximately 240 mL of water. Up to an additional 240 mL of water will be allowed, if necessary, to aid in swallowing of the study drugs. Subjects will not engage in strenuous activity at any time during the treatment period. When morning blood draws are required, study drug will be administered after blood sample collection. Study drug may be taken with or without food. The timing of TID dosing is provided in [Section 3.1.2](#) and the timing of BID dosing is provided in [Section 3.1.3](#). Doses of AT-752 and matching placebo should be separated by 8 hours ( $\pm 2$  hours) for TID dosing and by 12 hours ( $\pm 2$  hours) for BID dosing. After Day 1, if a dose is delayed, it should be taken as soon as possible, but must be taken at least 6 hours before the next scheduled dose. Otherwise, the dose must be skipped and the next dose taken as scheduled. Study drug dose modifications are not permitted in the study.

Dosing will be stopped at the end of the 15-dose (TID) or 10-dose (BID) treatment period. At the end of treatment period, tablets corresponding to any missed doses should be returned to the site.

Subjects must take the dose that was assigned at randomization, unless they discontinue for one of the reasons noted in [Section 4.3.1](#).

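### The BID clock-time examples in Protocol 3.1.3 include dose times that break the interval rules they illustrate

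*Protocol*

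**What the plan says.** Protocol 3.1.3 (Timing of BID Dosing) gives two interval rules.

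- First to second dose: "The second dose of study medication must be taken after at least 6 hours and no later than 12 hours after the first dose".
- General spacing: "Doses of study drug should be separated by 12 hours", with a tolerance of ± 2 h, so 10 to 14 h. Protocol 3 and 5.1 give the same BID spacing.

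Three clock-time examples follow.

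- Example 1 covers patients who start from 6 AM to 1 PM. Its instruction reads: "the second dose should be administered between 6 PM and no later than 10PM on Day 1".
- Example 2 covers patients who start from 1 PM to 4 PM. Its instruction reads: "the second dose should be administered at 10 PM on Day 1, and then the subject can begin their preferred 12-hour dosing schedule". That schedule starts the next day.
- Example 3 covers patients who start from 6 PM to 10 PM. Their 12-hour schedule begins on Day 2, so the second dose is the first one on Day 2.

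All three examples list the same Day 2 schedules, starting at 6 AM, 7 AM or 8 AM, as illustrations and not as a closed list. Each ends with a proviso that the 12 h ± 2 h timing be kept.

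**The concern.** Clock-time examples are what site staff and patients are likely to work from, because they turn an interval rule into times of day. Here the rule is worded as a requirement, and the examples are offered to show how to meet it. If the printed times can fall outside the rule, a site may commit a dosing deviation while doing what the protocol shows. Someone checking the same dose times later could classify them differently depending on which sentence they apply.

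The issue is confined to BID dosing. Cohort 3 is planned as BID, at up to 1500 mg per dose. Cohort 2 may be BID or TID. Cohort 1 is TID and is not affected.

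**Working it through.** The check is clock arithmetic. All inputs are the windows in Protocol 3.1.3.

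- Shortest interval = earliest later dose − latest earlier dose.
- Longest interval = latest later dose − earliest earlier dose.

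**Control: the TID section.** The same arithmetic on the five first-dose examples in Protocol 3.1.2 gives first-to-second intervals of 6–8, 6–8, 8–10, 6–10 and 8–10 h. All lie inside the 6 to 10 h rule stated there, so the method does not manufacture conflicts.

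**BID, first to second dose (rule: 6 to 12 h)**

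| Example | First dose | Second dose | Shortest | Longest | Inside 6–12 h? |
|---|---|---|---|---|---|
| 1 | 6 AM–1 PM | 6 PM–10 PM | 1 PM to 6 PM = 5 h | 6 AM to 10 PM = 16 h | No, at either end |
| 2 | 1 PM–4 PM | 10 PM | 4 PM to 10 PM = 6 h | 1 PM to 10 PM = 9 h | Yes |
| 3, 6 AM start | 6 PM–10 PM | 6 AM Day 2 | 8 h | 12 h | Yes |
| 3, 7 AM start | 6 PM–10 PM | 7 AM Day 2 | 9 h | 13 h | Not at the upper end |
| 3, 8 AM start | 6 PM–10 PM | 8 AM Day 2 | 10 h | 14 h | Not at the upper end |

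To see how much of Example 1 is affected, take every pair of times on a 15-minute grid: 29 first-dose times × 17 second-dose times = 493 pairs. Of these, 10 are under 6 h and 136 are over 12 h. The remaining 493 − 10 − 136 = 347 (347/493 = 70%) are compliant. This describes the printed windows. It does not forecast when patients will be dosed. A patient starting at 6 AM meets the rule only with a second dose at exactly 6 PM, although the window runs to 10 PM.

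**BID, second to third dose (spacing: 10 to 14 h)**

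Example 2 fixes the second dose at 10 PM, so the listed Day 2 starts give:

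- 10 PM to 6 AM = 8 h, outside
- 10 PM to 7 AM = 9 h, outside
- 10 PM to 8 AM = 10 h, inside at the limit

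Example 1 gives the same 8 h or 9 h if its second dose is taken at 10 PM and the Day 2 schedule starts at 6 AM or 7 AM.

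**Can the proviso reconcile these?**

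- It cannot govern the first-to-second interval in Example 2, because that example requires 6 to 9 h there. Reading it as a limit on the same interval in Example 1 would therefore be inconsistent.
- For the second-to-third interval in Example 2, it excludes two of the three starts listed in its own sentence.
- In Example 3 its upper bound of 14 h exceeds the 12 h maximum for the second dose.

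**The case against.** The strongest reply is that the texts can be satisfied together. The 6 to 12 h limit is mandatory, whereas the examples are illustrations in softer wording and can be read inside it. A compliant path exists at the limits of each first-dose window:

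- 6 AM start: second dose 6 PM (12 h), third 6 AM (12 h).
- 1 PM start under Example 1: second dose 7 PM (6 h), third 6 AM (11 h).
- 1 PM to 4 PM start under Example 2: second dose 10 PM (6 to 9 h), third 8 AM (10 h).
- 6 PM start: second dose 6 AM (12 h).
- 10 PM start: second dose 8 AM (10 h).

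This stands. A reader might infer that sites must break either the rule or the example, and the documents do not support that. Nor do the examples plainly permit an 8 h interval: it is listed, but subject to a proviso that excludes it. The 5 to 16 h span belongs to Example 1 alone.

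Three further inferences are tempting and do not hold.

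- **The late-dose rule is another contradiction.** Protocol 3.1.3 and 5.1 say a delayed dose "must be taken at least 6 hours before the next scheduled dose", which on a 12-hour schedule could mean up to 6 h late. That rule says what to do once a dose has missed its time, so it necessarily operates outside the target window.
- **BID intervals are uncontrolled.** Spacing after the first interval is stated consistently as 12 h ± 2 h in Protocol 3, 3.1.3 and 5.1.
- **The per-protocol set cannot be defined, or the results are compromised.** SAP 4.3 excludes patients for major violations affecting safety or data quality, and nothing makes every off-window dose a major one. The primary population is mITT, which does not depend on dose timing. PK parameters use actual sampling times (SAP 11.2), and dose times are recorded and listed (Protocol 5.5, SAP 7.3).

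What the reply does not remove is that the printed windows go beyond the rule, and that a reader must work out which printed combinations to avoid.

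**Conclusion.** The point holds as an inconsistency within Protocol 3.1.3. Example 1 spans 5 to 16 h against a mandatory 6 to 12 h. Two of the three Day 2 starts listed in Example 2 (8 h and 9 h) conflict with the 10 to 14 h proviso attached to them. Example 3 can reach 13 or 14 h against a 12 h maximum.

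The defect is loosely drawn windows, not rules that cannot be followed together. Its likely effect is avoidable dosing deviations and some ambiguity in classifying them. It does not invalidate the primary analysis or the PK analysis.

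The conclusion assumes that the printed clock times are meant literally and that the 6 to 12 h limit applies to every BID first-to-second interval, including evening starts. If evening starters were meant to be exempt, the Example 3 conflict would go, but the text gives no such exemption. Part of the compliance section (Protocol 5.5) is redacted, so a deviation threshold may be stated there. That would not change the conflict inside 3.1.3.

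**What to change.** Before any BID cohort opens, reconcile three parts of Protocol 3.1.3: the first-to-second dose rule, the clock-time examples with their listed Day 2 starts, and the 12 h ± 2 h proviso. Every combination of times shown should satisfy the stated rules, and the text should say which interval the proviso governs. Which interval is right is for the sponsor to decide, and none is proposed here. The Day 1 interval, the later spacing and the late-dose rule need not be identical. They need only be stated so that they do not conflict.

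Dosing-time deviations in BID cohorts should then be judged against the reconciled text.

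The cost is a wording change to the protocol, with the usual amendment approvals. No analysis, sample size or data collection changes.
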